	
than in replacement or stress doses as described in Inclusion Criterion No.5) within 90 days prior to or throughout screening.
 
Note: Stable doses of inhaled, intra-articular, or topical corticosteroids are permitted.
 
15. Currently using or have used within 26 weeks prior to screening any weight-loss or appetite-suppressive medications including orlistat, zonisamide, lorcaserin, bupropion, topiramate, sibutramine, stimulants (eg, phentermine or ADHD medications such as methylphenidate or amphetamines), glucagon-like peptide-1 (GLP-1) receptor agonists (eg, dulaglutide, exenatide, liraglutide, lixisenatide, semaglutide), sodium-glucose cotransporter-2 (SGLT-2) inhibitors (eg, canagliflozin, dapagliflozin, empagliflozin, sotagliflozin) or medications that affects IGF-1 or GH measurements including cabergoline at doses above 0.5 mg weekly or bromocriptine at doses above 20 mg weekly
 
Note: if it can be documented that no weight-loss occurred with these drugs, a 90-day withdrawal period prior to screening is sufficient.
 
16. Known history of hypersensitivity and/or idiosyncrasy to any of the test compounds (somatropin) or excipients employed in this trial.
 
17. Known history of neutralizing anti-hGH antibodies
 
18. Inability to undergo scanning by DXA or a non-interpretable DXA scan at screening
 
19. Female who is pregnant, breast-feeding or intends to become pregnant or is of childbearing potential (i.e., fertile, following menarche and until becoming post-menopausal unless permanently sterile) and not using adequate contraceptive methods
 
• Acceptable highly effective methods of contraception include intrauterine device (IUD); intrauterine system (IUS); bilateral tubal occlusion (must be documented); combined or progestogen-only hormonal contraception associated with inhibition of ovulation; vasectomized partner (must be documented); or sexual abstinence (only when it is the usual and preferred lifestyle of the subject)• Clinically acceptable methods of birth control include male or female condom with or without spermicide; progestogen-only oral hormonal contraception, where inhibition of ovulation is not the primary mode of action; or cap, diaphragm, or sponge with spermicide.• Permanent sterilisation methods include hysterectomy, bilateral salpingectomy, and bilateral oophorectomy.
--	---

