19. Female who is pregnant, breast-feeding or intends to become pregnant or is of childbearing potential (i.e., fertile, following menarche and until becoming post-menopausal unless permanently sterile) and not using adequate contraceptive methods

- Acceptable highly effective methods of contraception include intrauterine device (IUD); intrauterine system (IUS); bilateral tubal occlusion (must be documented); combined or progestogen-only hormonal contraception associated with inhibition of ovulation; vasectomized partner (must be documented); or sexual abstinence (only when it is the usual and preferred lifestyle of the subject).
- Clinically acceptable methods of birth control include male or female condom with or without spermicide; progestogen-only oral hormonal contraception, where inhibition of ovulation is not the primary mode of action; or cap, diaphragm, or sponge with spermicide.
- Permanent sterilization includes hysterectomy, bilateral salpingectomy, and bilateral oophorectomy.

Note: Females of childbearing potential must accept to use the above-mentioned methods of contraception from the beginning of screening to the last trial visit.

Note: Periodic abstinence (e.g., calendar, ovulation, symptothermal, post-ovulation methods) and withdrawal are not acceptable methods of contraception.

Note: For subjects using oral combined hormonal contraception (ie containing estrogen), the dose and route must be stable for ≥ 6 weeks prior to screening and throughout the trial

20. Male subjects must use a condom, or his female partner of childbearing potential must use an effective form of contraception as described above, from the beginning of screening to the last trial visit.

21. Known substance abuse or known (or previous) eating disorders, including anorexia nervosa, bulimia and severe gastrointestinal disease affecting normal eating (as judged by the investigator).

22. Any disease or condition that, in the judgement of the investigator, may make the subject unlikely to comply with the requirements of the trial or any condition that presents undue risk from the investigational product or procedures.

23. Participation in another interventional clinical trial involving an investigational compound within 26 weeks prior to screening or in parallel to this trial.

24. Currently using or have used within the last 3 days prior to screening: biotin >0.03 mg/day from supplements

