10.2.2. Treatment Period

Randomized subjects will receive the study drug as assigned according to randomization and dosing group (Section 9). The trial procedures are indicated in the Schedule of Events (Section 18.2), Table 5, and detailed description in Section 11.

Visit 3 may be conducted via phone call per investigator's discretion, the following procedures are conducted at each visit (Visit 1 – Visit 7) if not otherwise indicated.

Table 5: Treatment Period Procedures

Assessment	Details and Comments
Concomitant medications and AEs	Visit 1 through Visit 7. If phone call (Visit 3): discussion only.
Subject Diary review	Visit 2 through Visit 7. If phone call (Visit 3): discussion only.
Weight	Visit 1 through Visit 7. Not required if Visit 3 is conducted via phone.
Physical examination and vital signs	Visit 1 through Visit 7. Not required if Visit 3 is conducted via phone.
12-lead ECG	Visit 1 and Visit 7 – all treatment arms; local reading. Weekly treatment arms will have an additional ECG assessment at 1-3 days post-dose at Visit 6, local reading.
Fundoscopy	Visit 7
Safety laboratory assessments	Visit 1 through Visit 7. Not required if Visit 3 is conducted via phone. Fasting status is required. Routine chemistry and hematology, hormone status, glycemic status, lipid panel (see Section 11.9).
Blood sampling for IGF-1 and IGFBP-3 assessments	Visit 1 through Visit 7. Not required if Visit 3 is conducted via phone. Data will be reviewed, and dose titration guidance provided by unblinded team member, results will not routinely be distributed to the site staff.
Pregnancy test for females of childbearing potential	Visit 1 through Visit 7 and approximately at least 30 days after last study drug dose for subjects not participating in the extension trial. Not required if Visit 3 is conducted via phone. Blood test at central laboratory. Additionally, urine dipstick test at Visit 1 prior to the first dose and at any time during the trial if a menstrual period is missed. Pregnancy testing will not be required for women who have undergone a hysterectomy or bilateral tubal ligation, or for women above the age of 50 who have been without a menstrual period for at least 12 months.

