11.9.1. Pregnancy Test

Testing for hCG should be performed at every on-site visit for female subjects of childbearing potential. A blood test will be run with every safety laboratory analysis run. Additionally, subjects will complete a urine dipstick test prior receiving the first dose of the study drug and at any time during the trial if a menstrual period is missed.

Pregnancy testing will not be required for women who are surgically sterile (for example have undergone a hysterectomy or bilateral tubal ligation), or for women above the age of 50 who have been without a menstrual period for at least 12 months.

Subjects who are sexually active must use an effective form of contraception.

See Section [9.6.3](#) and Section [12.4.1](#) for actions in case of pregnancy during the trial conduct.

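### Table 5 and Section 11.9.1 treat tubal ligation as sterility and waive pregnancy tests, whereas Exclusion Criterion 19 treats tubal occlusion as contraception

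*Protocol*

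**What the plan says.** Exclusion Criterion 19 (Protocol 8.1.2, repeated in the Synopsis) defines childbearing potential as "fertile, following menarche and until becoming post-menopausal unless permanently sterile". It then sorts procedures into separate lists.

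- Contraception: "Acceptable highly effective methods of contraception include intrauterine device (IUD); intrauterine system (IUS); bilateral tubal occlusion (must be documented", among others.
- Sterilization: "Permanent sterilization includes hysterectomy, bilateral salpingectomy, and bilateral oophorectomy". The Synopsis has the same three procedures: "Permanent sterilisation methods include hysterectomy, bilateral salpingectomy, and bilateral oophorectomy".

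The testing rules are in several places.

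- Section 11.9.1 gives the general rule: "Testing for hCG should be performed at every on-site visit for female subjects of childbearing potential".
- The Schedule of Events (18.2, reproduced as SAP Table 1) marks a test at screening and at Visits 1 to 7 for females of childbearing potential. Visit 3 is excused if held by phone.
- Sections 10.2.2.1, 10.2.2.2 and 10.2.5 and Schedule footnote k add a test about 30 days after the last dose for women who do not enter the extension.
- Table 5 (10.2.2) repeats these tests, specifies blood, and adds a dipstick: "Additionally, urine dipstick test at Visit 1 prior to the first dose". Table 5 and 11.9.1 also ask for a dipstick whenever a period is missed.

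The waiver appears in two of these places. Table 5 states: "Pregnancy testing will not be required for women who have undergone a hysterectomy or bilateral tubal ligation". Section 11.9.1 waives testing for women who are "surgically sterile (for example have undergone a hysterectomy or bilateral tubal ligation". Both also exempt women above 50 with no period for at least 12 months.

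**The concern.** The same woman is a contraceptive user in the eligibility text and sterile in the testing text. If the eligibility definition is applied, she is tested at every on-site visit. If the waiver is applied, she has no required test after screening, not even before the first dose. A woman with an intrauterine device, which sits in the same highly effective category, is tested throughout.

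Pregnancy status matters here for three reasons: pregnancy is an exclusion (8.1.2), it is a required reason to stop study drug (9.6.3), and DXA cannot be performed when pregnancy is present or suspected (11.12). Two sites relying on different sections could handle identical women differently.

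**Working it through.** **Step 1: how is a woman with tubal ligation classified?**

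| Place | Tubal occlusion or ligation | Hysterectomy | Salpingectomy, oophorectomy |
|---|---|---|---|
| Exclusion 19 | contraception, if documented | permanent sterilization | permanent sterilization |
| Table 5 | testing waived, no mention of documentation | testing waived | not named |
| 11.9.1 | example of surgical sterility, testing waived | example of surgical sterility, testing waived | not named |

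Only hysterectomy is treated alike in all three. The waivers name a procedure that Exclusion 19 puts under contraception and omit two of the three that it puts under sterilization. That pattern suggests lists that were never aligned. Two inferences are needed: that ligation is a form of occlusion, and that the sterilization list, although worded as inclusive, does not cover a procedure expressly placed in the other list.

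**Step 2: how many tests does this concern?** The count is per completer, after screening. Unscheduled missed-period dipsticks are left out.

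Waived if Table 5 and 11.9.1 govern = blood tests + Visit 1 dipstick + post-treatment test:

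- Minimum (Visit 3 by phone, woman enters the extension): 6 + 1 + 0 = 7
- Maximum (Visit 3 on site, no extension): 7 + 1 + 1 = 9

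Called for by places with no waiver (Schedule row and footnote k, 10.2.2.1, 10.2.2.2, 10.2.5) = visit tests + post-treatment test:

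- Minimum: 6 + 0 = 6
- Maximum: 7 + 1 = 8

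The difference is 7 − 6 = 9 − 8 = 1. It is the Visit 1 dipstick, which appears only in Table 5 and 11.9.1.

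The 6 to 8 are tests with no stated specimen. For Visits 1 to 7, blood is specified only in Table 5 and 11.9.1, the two places that carry the waiver.

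**Step 3: how many women?** The documents give no figure for tubal ligation, so the number affected cannot be calculated.

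**The case against.** The strongest defence is that there is no operational conflict. Section 10.2.2 points the reader to the Schedule, Table 5 and Section 11 together, and the two detailed sources give the same answer. The Table 5 waiver sits inside the row on females of childbearing potential, as an exception to it. The Schedule row is also silent on the hysterectomy and over-50 exemptions, and nobody would call that a contradiction. None of the places without a waiver mentions ligation. Waiving repeat hCG after a documented, highly effective procedure is a defensible choice, and the screening list in 10.2.1 asks for serum hCG in females without qualification.

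Most of this stands. A reader might infer that the Schedule flatly requires serum tests in women with tubal ligation and that the waiver contradicts it. The documents do not support that: the Schedule names neither the specimen nor the procedure, and Table 5 and 11.9.1 can be read as a specific exception.

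What the defence does not remove is the difference in definition. Section 10.2.2 sets no order of precedence among the three sources. Even if the waiver governs, it rests on calling sterile a woman whom Exclusion 19 classes as using contraception, and it leaves out the documentation condition. The hysterectomy exemption raises no such question, because Exclusion 19 also counts hysterectomy as sterilization.

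**Conclusion.** The mismatch is real and minor. Exclusion 19 is most naturally read as treating a premenopausal woman with tubal ligation as of childbearing potential, while Table 5 and 11.9.1 treat her as sterile and drop 7 to 9 scheduled tests per completer, 6 to 8 of which other sections call for without a waiver. This rests on equating ligation with occlusion and on the placement of occlusion under contraception.

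A reader might go further and infer a material safety gap or a threat to the DXA endpoint. The documents do not support that. The protocol itself rates documented occlusion as highly effective, a test that is not required may still be done, screening hCG is unaffected, and DXA is barred on suspicion alone. Few women are likely to be affected, although their number is unknown. Power and the primary analysis do not change.

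**What to change.** Use one definition, that of Exclusion Criterion 19.

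- In Table 5, replace hysterectomy or bilateral tubal ligation with: *hysterectomy, bilateral salpingectomy or bilateral oophorectomy*.
- In 11.9.1, replace the reference to surgical sterility and its bracketed examples with: *permanently sterile as defined in Exclusion Criterion 19 (hysterectomy, bilateral salpingectomy or bilateral oophorectomy)*. The words introducing the list as an example must go. Otherwise a site could still count ligation as surgical sterility and skip testing.
- Keep the over-50 exemption and the screening rule as they are.

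Stating the exemption for documented occlusion in Exclusion 19 and the Schedule would be equally consistent. Testing is preferable because it is cheap, restores the check before the first dose, and treats these women like intrauterine device users.

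The cost is a few extra hCG assays, mostly on blood already drawn at on-site visits or at the post-treatment antibody draw, plus some dipsticks. Section 15.9 requires a documented amendment with ethics approval and, as required, regulatory approval, across about 120 planned sites. The edit does not justify an amendment of its own and can be bundled with the next one.

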10.2.2.1. Visit Schedule of Weekly Treatment Arms (Lonapegsomatropin/Placebo)

1. Visit 1 will be performed on the day of the 1st dose (Week 1, Day 1) and all assessments will be done pre-dose, except for the injection site reaction assessment. The first dose will be given on site.
2. Visit 2 (Week 4) and Visit 3 (Week 8) will be conducted approx. 4 - 5 days post-dose (96-120 h post-dose +/- 3 hours) to be able to assess the average IGF-1 level (IGF-1 SDS) to support dose titration.
3. Visit 4 (Week 12) will be conducted approx. 4 - 5 days post-dose (96-120 h post-dose +/- 3 hours) to be able to assess the average IGF-1 level (IGF-1 SDS) to support dose titration. Subjects will be assigned their fixed dose for the next 26 weeks.
4. Visit 5 (Week 17, +/- 1 week) will be conducted on the day of the 17th dose (+/- 1 dose) to have a steady-state trough value and the upcoming dose given on site (144 – 168 h after the prior dose +/- 3 hours). All assessments (except for injection site reaction assessment) are suggested to be done pre-dose.
5. Visit 6 (Week 28, +/- 1 week) will be conducted 1-3 days post-dose (24-72 h post-dose +/- 3 hours) to have a maintenance phase sampling at approximate peak hGH and peak IGF-1 (IGF-1 SDS).
6. Visit 7 (Week 38, + 1 week, end of trial) will be conducted approx. 4 - 5 days post-dose (96-120 h post-dose +/- 3 hours) to be able to assess the average IGF-1 level (IGF-1 SDS) at the end of the trial. For subjects not participating in the extension trial: A phone call will be conducted up to 2 weeks after this visit to assess if ongoing AEs are closed. An ADA and a pregnancy test for females of childbearing potential sample will be collected approximately at least 30 days after the last study drug dose.

10.2.2.2. Visit Schedule of Daily Somatropin Treatment Arm

1. Visit 1 will be performed on the day of the 1st dose (Week 1, Day 1) and all assessments will be done pre-dose, except for the injection site reaction assessment. The first dose will be given on site.
2. Visit 2 (Week 4) and Visit 3 (Week 8) will be conducted at any day of the week.
3. Visit 4 (Week 12) will be conducted at any day of the week. Subjects will be assigned their fixed dose for the next 26 weeks. This dose may be given on site or at the subject's home.
4. Visit 5 (Week 17, +/- 1 week) and Visit 6 (Week 28, +/- 1 week) will be conducted at any day of the week.
5. Visit 7 (Week 38, + 1 week, end of trial) will be conducted the day after the 26th week (or 27th week) of fixed dosing is completed. For subjects not participating in the extension trial: A phone call will be conducted up to 2 weeks after this visit to assess if ongoing AEs are closed. An ADA and a pregnancy test for females of childbearing potential sample will be collected approximately at least 30 days after the last study drug dose.

10.2.3. Unscheduled Visits

Unscheduled visits are those visits that occur between regularly scheduled visits and are performed to assess a previously or currently noted AE, abnormal laboratory value(s), and/or clinical findings. In such cases, the subject will be contacted to arrange an unscheduled visit. Only focused assessments (guided by the reason for the visit) will occur at these visits. Unscheduled dose titrations may be communicated via phone and do not necessarily require an on-site visit.

10.2.4. Early Termination Visits

Early termination is when a subject's trial participation discontinues prior to completion of the trial. If trial participation is discontinued prematurely, an Early Termination Visit (procedures indicated for Visit 7 in the Schedule of Events table, as applicable) will be performed. The site staff should aim to collect AE / SAE and outcome data up to two weeks after the last study drug dose and an ADA sample approximately 30 days after the last study drug dose, either during the Early Termination Visit or a follow-up phone call (AE / SAE collection only).

For subjects who discontinue the study drug for reasons related to safety, unblinding of the treatment assignment for the subject may occur if deemed necessary by the Sponsor to assess a potential safety signal or by the investigator to provide adequate medical care to the subject.

10.2.5. Follow-up

Follow-up Period is treatment free period when trial subjects will not be receiving any hGH treatment which is applicable only for the subjects who will not continue into the extension trial. Two weeks after Visit 7 (Week 40), the site will have a follow-up phone call with the subject to review AEs / SAEs (See Section 12.3.2). An ADA and for females of childbearing potential a pregnancy test sample will be collected approximately at least 30 days after the last study drug dose (Week 42).

10.2.6. Home Visits / Virtual Visits

With Sponsor agreement, home visits and / or virtual visits may be conducted in place of in-person on-site visits for visits which do not require assessments to be performed on site. Home visits and / or virtual visits may also be permitted after Sponsor's approval in case of restrictions for subjects and / or physicians to access or enter the sites. Examples include, but are not limited to, shut-downs by the government, viral outbreak, natural disaster and / or significant safety risk.

11. ASSESSMENTS

11.1. SUBJECT DIARY

The Subject Diary will be provided / explained to the subject at the clinic visits and should be completed on the day of the study drug administration (weekly for lonapegsomatropin/placebo and daily for the daily somatropin arm). The data captured within the Subject Diary include:

- Date and time of the study drug administration
- Dose of the study drug
- Location of injection site

The subject will also have a chance to record an assessment of the injection site and changes to medications or subject's health.

The Subject Diary should be reviewed by trial staff at every trial visit as part of concomitant medication review, AE reporting and the study drug compliance confirmation.

11.2. WEIGHT MEASUREMENT

Weight should be measured at each on-site visit at approximately the same time of day using the same calibrated weight scale throughout the trial as possible (to minimize bias and reduce variability). Subjects should be wearing light clothing and no shoes for weight measurement at all visits.

11.3. HEIGHT MEASUREMENT

Height should be measured at screening on a stadiometer. Subjects should be wearing light clothing and no shoes.

11.4. PHYSICAL EXAMINATION

A physical examination of the following body systems should be performed:

- General appearance
- Integumentary (including injection site reaction assessment, see Section [11.13](#))
- Head, ears, eyes, nose, throat
- Neck / thyroid
- Lymphatic
- Cardiovascular
- Respiratory
- Abdomen
- Genitourinary
- Nervous system
- Musculoskeletal
- Extremities

11.5. VITAL SIGN MEASUREMENTS

Subject should rest for at least 5 minutes before assessment. The following vital signs should be measured:

- Heart Rate
- Blood Pressure
- Respiratory Rate
- Body Temperature

11.6. MRI / CT SCAN

An MRI scan is required at screening if a pituitary MRI scan from within 6 months prior to screening is not available. A CT scan can be used if MRI scan is contraindicated. An MRI scan is required at the end of trial for childhood cancer survivors.

11.7. 12-LEAD ECG

Local ECG readings and assessments will be conducted at screening, Visit 1, and Visit 7. For weekly treatment arms (lonapegsomatropin and placebo), an additional local ECG will be done at Visit 6.

11.8. FUNDOSCOPY

Fundoscopy is required for all subjects at screening and at Visit 7.

For subjects with a diagnosis of diabetes mellitus at screening, fundus photography is required at screening and Visit 7.

11.9. LABORATORY ASSESSMENTS

Blood will be collected at each on-site visit for assessments as listed in the Schedule of Events (Section 18.2). As described in Section 10.2, fasting is required. If not otherwise indicated, the routine chemistry and hematology assessments will include:

- Chemistry: sodium, potassium, calcium, chloride, total bilirubin, alkaline phosphatase, lactate dehydrogenase (LDH), aspartate aminotransferase (AST), alanine aminotransferase (ALT), gamma-glutamyl transferase (GGT), albumin, total proteins, creatinine (also eGFR rate calculation per MDRD equation), urea-nitrogen, uric acid, ferritin and transferrin
- Hematology: hemoglobin, erythrocyte count, hematocrit, mean corpuscular hemoglobin (MCH), mean corpuscular volume (MCV), mean corpuscular hemoglobin concentration (MCHC), leukocytes, differential blood count of leukocytes, platelet count
- Glucose metabolism: fasting insulin, fasting glucose, HbA1c
- Lipid metabolism (fasting): total cholesterol, triglycerides, high-density lipoprotein (HDL), low-density lipoprotein (LDL), Lp(a) lipoprotein, free fatty acids, very low-density lipoprotein (VLDL)

- Thyroid and adrenal status: TSH, fT4, and fT3 and morning (06:00-10:00AM) serum cortisol. Subjects who are not on glucocorticoid replacement therapy and are diagnosed with low morning cortisol may undergo an ACTH stimulation test including timepoint zero / baseline sample at any time during the trial
- Testosterone (males only): at Visits 1, 4, 6 and 7

The total blood volume collected in any 90-day-period during the trial will be up to approximately 100 mL. The total blood volume over 48 weeks of trial duration will not exceed 300 mL.

Blood samples will be analyzed at central and specialized laboratories in Germany, Sweden, and the US. The samples will be destroyed when analyses are final, except for samples collected for antibody measurements which may be stored up to five years after study end in order to allow additional antibody testing and characterization upon request from health authorities. This storage will be in Sweden and/or the US.

Detailed blood sampling, processing and assaying of samples will be provided in the Laboratory Manual.

